7.5. Early Discontinuations

Data to be Collected

If the study participation has to be terminated early by the investigators (due to safety concerns), or if a participant chooses to withdraw from the study, including the case of not showing up for scheduled visits on site (Visits 1, 2, 3, 5, 6), the data collected to date will not be included for the cognitive and sleep-EEG outcomes and the participant will be replaced. However, early discontinuation will be included in the data set for the feasibility outcomes as appropriate. Visits 4 and 7 are not mandatory for study completion.

Criteria for Intervention Discontinuation

An investigator may discontinue or withdraw a participant from the study for the following reasons:

- Any clinical adverse event (AE), intercurrent illness or other medical condition, or situation occurs such that continued participation in the study would not be in the best interest of the participant.

- The participant meets any exclusion criteria (either newly developed or not previously recognized) or a reason for immediate early termination of participation.

7.6. Enrollees May Drop Out

Participants may voluntarily withdraw from participation at any time, for any reason, with no penalty or loss of rights. In case of no-show, an attempt will be made to contact the participant (by mail or phone). The reasons for drop-out and missing data will be documented in the database.

8. Statistical Analysis Plans

8.1. Strategies that Apply to all the Aims

All testing described below assumes a significance threshold of $p = 0.05$. Analyses will be deemed to be statistically significant if the p-value is less than this threshold. An analysis that does not exceed this threshold will be considered inconclusive. The proposed statistical analysis strategy acknowledges that no p-value can reveal the plausibility, presence, truth, or importance of an association or effect.

There may be additional covariates included in the analysis. Data will be assessed for normality and, if deemed necessary, corrective procedures will be applied (e.g., log normalization). This correction will be applied upon consideration of the variables themselves, and not based on the result of the intended analysis.

8.2 Sample Description

The sample will be described using the following parameters: Age, sex, racial/ethnic categories, education, living conditions, work status, clubs/social organizations, sports, social contacts, media consumption, caffeine and alcohol consumption, smoking status. Whenever feasible, graphical methods will be used to describe the sample. Continuous data will be described using means, standard deviations, and confidence intervals, while categorical data will be described using counts/percentages.

8.3 Aim-Specific Plans

Plans for Aim 1.

a) The proportion of participants in which stimulation and cognitive testing could be completed will be calculated after both stimulation sessions, i.e. visit 2 and visit 4 (percentage and 95% confidence interval).

Plans for Aim 2.

To evaluate the effect of gamma-tACS on cognitive testing.

a) Primary outcome: Ultra-delayed verbal memory recall (i.e. amount of words and word associations remembered the day after encoding the RAVLT) after gamma-tACS compared to after control stimulation, intra- and interindividually.

We will perform a two-way or one-way repeated measure ANCOVA with time (baseline and post-treatment) and treatment (control vs gamma-tACS) as within-subjects factors, and the order in which tACS will be applied (tACS-sham or control tACS) as covariate. Post-hoc tests will be calculated after Bonferroni correction for multiple comparisons.

Null hypothesis: There is no difference between tACS and control stimulation for ultra-delayed memory recall one day after stimulation. Alternative hypothesis: Memory recall is better after gamma-tACS than after control stimulation.

b) Secondary outcomes: Verbal and associative learning (immediate and delayed recall, recall after 5 days) and executive functions (results of Letter Fluency, Stroop Test, Trail Making Test, Tests of Attentional Performance), comparison intra- and interindividually, after gamma-tACS and control stimulation (comparison of difference

between visit 1-visit 2 and visit 3-visit 4; comparison of absolute results of visit 1 versus visit 3 and visit 2 versus visit 4; statistical tests and covariates as in a)).

Hypotheses are the same as for the primary outcome.

Plans for Aim 3.

To investigate the feasibility and adherence to wearable device (single-channel EEG during the night).

a) The proportion (percentage and 95% confidence interval) of participants with at least four hours of EEG recording in the first night.

b) The proportion (percentage and 95% confidence interval) of participants with at least four hours of recorded nocturnal data for each of all three nights.

Plans for Aim 4.

To evaluate the effect of gamma-tACS compared to control stimulation on sleep EEG. Differences (individual level and group level, statistical tests as mentioned above) of sleep latency (minutes from lights out to sleep onset), sleep efficiency (sleep duration in relation to time spent in bed), sleep spindle frequency (maximum number per hour) and slow wave activity (maximum minutes of slow wave sleep per hour).

The statistical method will be the same as for Aim 2.

Null hypothesis: Sleep EEG does not change after gamma-tACS compared to the night after control stimulation.

Alternative hypothesis: There is a higher amount of sleep spindles and/or slow wave sleep after gamma-tACS (compared to the control).

Plans for Aim 5.

To investigate whether there is a correlation (Pearson's) between the stimulation-induced changes in cognitive testing scores and sleep EEG features after gamma-tACS versus after control stimulation (on individual and group level). This is an exploratory analysis.

Plans for Aim 6.

Comparison of cognitive test results after stimulation and sham on individual and group level using ANCOVA (see CT.gov). This is an exploratory analysis.

Plans for Aim 7. To investigate whether there is a correlation (Pearson's) between the stimulation-induced changes in motor activity features (according to the wristband accelerometer results) after stimulation in general and after gamma-tACS versus after control stimulation (on individual and group level). This is an exploratory analysis.

Plans for Aim 8.

To investigate whether there is a correlation (Pearson's) between the motor threshold (TMS) and the subjective symptoms during tACS. This is an exploratory analysis.

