| Numbers of Enrollees | This pilot study requires n = 28 participants who complete all aspects of the protocol. Participants are recruited and enrolled until this target is reached. We anticipate screening up to 100 participants and enrolling up to 50 participants. |

| | |
|--|---|
| Intervention | 
This is a single-center prospective interventional control controlled cross-over pilot study.
 
The intervention consists of the application of tACS stimulation in the gamma-frequency range during approximately one hour of cognitive testing.
 |
| Outcome Measures | 
Aim 1: Cognitive testing during tACS completed in >80% of participants.
 
Aim 2: Participants will memorize 15 words ("Rey Verbal Learning Test", (a)) and 8 word-pairs (associative verbal memory, (b)) during gamma-tACS and control tACS. They will be required to recall the words after a short delay on the same day, on the day after and after 5 days ("ultra-delayed recall"). The number of correctly remembered words (a) and word-pairs (b) will be recorded.
 
Aim 3: Feasibility (a) will be considered feasible if the device has been worn for at least 4 hours during the first night for >/= 80% of participants. Acceptability (b) will be considered as given if the device has been worn for at least 4 hours during each of the three nights in >/=80% of participants.
 
Aim 4: Amount of sleep spindles (a) and slow wave sleep (b) during sleep recording.
 
Aim 5: Exploration of correlation between memory recall performance and sleep EEG features (especially spindles, slow waves). Difference in recall scores (verum versus sham tACS) will be correlated with differences in sleep EEG features (verum versus sham tACS).
 
Aim 6: For (a) the number of correct words, of perseverations and of rule breaks will be calculated. For (b) and (c) time for test completion and errors will be calculated. For (d) percentile ranks for the following subtests will be calculated: Alertness, Go/NoGo, Divided Attention, Visual Scanning.
 
Aim 7: Exploration of correlation between amount of motor activity/inactivity phases (measured by actigraphy watch) and stimulation versus no stimulation as well as gamma- versus control stimulation.
 
Aim 8: Exploration of correlation between the TMS motor threshold and the maximal tolerated amplitude (according to the subjective symptoms) for tACS.
 |

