| Statistical Analysis Plans for Each Aim | 
Aim 1: Proportion (percentage and 95% confidence interval) of participants with completed cognitive testing during stimulation study session.
 
Aim 2: Comparison of memory and associative testing after stimulation and sham on individual and group level using ANCOVA.
 
Aim 3: Proportion (percentage, 95% confidence interval) of participants with at least four hours of EEG-data in the first night (a).Proportion (percentage,
 |

| | |
|-------------------------------|--|
| | 95% confidence interval) of participants who successfully collected at least four hours of EEG for all three study nights (b). Aim 4: Comparison of sleep spindles (a) and slow wave sleep (b) derived from sleep EEG for verum versus control tACS using ANCOVA. Aim 5: Exploratory investigation of correlations (Pearson's) between stimulation induced changes in memory recall performance and sleep EEG features. Aim 6: Comparison of test results after stimulation and sham on individual and group level using ANCOVA. Aim 7: Exploratory investigation of correlations (Pearson's) between changes in motor activity pattern before and after stimulation. Aim 8: Exploratory investigation of a correlation (Pearson's) between the level of the TMS motor threshold and the tolerated tACS level (lower level from 21 Hz and 40 Hz, based on subjective symptoms). |
| Study Duration | 1 year |
| Participation Duration | 2 weeks |
| Enrollment Duration | 6 months |

2. Introduction

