7.1. Table of Events

| Procedure | | Visit 0 screening (online/phone) | Visit 1 Baseline (from day after Visit 0 to +14 days) | Visit 2 (day after Visit 1) | Visit 3 (day after Visit 2) | Visit 4 (telephone; 5 days after Visit 2) | Visit 5 (6-9 days after Visit 2) | Visit 6 (day after Visit 5) | Visit 7 (telephone; 5 days after Visit 5) |
|--------------------------|---|----------------------------------|---|-----------------------------|-----------------------------|---|----------------------------------|-----------------------------|--|
| Recruitment | Informed consent | X (oral) | X (written) | | | | | | |
| | Eligibility assessments | X | X | | | | | | |
| | Enrollment and randomization | | X | | | | | | |
| Eligibility assessments | At least 4 hours of initial sleep-EEG | | | x | | | | | |
| | No epileptiform discharges in baseline-EEG | | x | | | | x | | |
| | No psychotropic treatment/illegal drugs within the last 3 months, no alcohol within the last 24 hours | | | x | x | | x | x | |
| Intervention | (Control) Stimulation | | | x | | | x | | |
| | Cognitive testing ¹ | | | x | x | x (only verbal memory and associative verbal memory recall) | x | x | x (only verbal and associative verbal memory recall) |
| | Sleep-EEG ² | | x (next night) | x (next night) | | | x (next night) | | |
| | Actigraphy | | x | x | x | x | x | x | |
| | TMS Motor Thresholding | | | x | | | | | |
| Patient Reported Outcome | Subjective tolerability of sleep EEG | | | x | x | | | x | |
| | Sleepiness (Karolinska Scale) | | | x | x | | x | x | |
| | Sleep quality | | | x | x | | x | x | |
| | Affect (PANAS) | | | x | x | | x | x | |
| Safety Monitoring | Assessment of AEs | | | x | x | x | x | x | x |

¹ Standardized results of: RAVLT (Rey Auditory Verbal Learning Test) (26), word association test, Letter Fluency (28), Stroop Color and Word Test (29), Trail Making Test A and B (30), TAP (Test of Attentional Performance) (31).

² Device worn (yes/no), hours of recording, sleep latency, sleep efficiency, amount of sleep spindles and slow wave sleep.

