7.3. Enrollment

Visits 0 and 1

The following procedures will occur:

1. Signing of informed consent
2. Completion of demographics and supplementary questions (mainly providing information about the cognitive state): Sex, racial/ethnic categories, education, living conditions, work status, clubs/social organizations, sports, social contacts, media consumption, concomitant medications list, caffeine consumption, alcohol consumption, smoking status.
3. Specific questionnaires to exclude patients with indications for a sleep disorder, depression, anxiety disorder, cognitive impairment, epilepsy:
 - 3.1 Sleep Quality Assessment PSQI (15): Screening for sleep disorders. Result: 0-21 points. Exclusion if >5 points.
 - 3.2 Patient Health Questionnaire-9 (16): Screening for depression. Result: 0-27 points. Exclusion if ≥5 points.
 - 3.3. General Anxiety Disorder-7 (17): Screening for anxiety disorder. Result: 0-21 points. Exclusion if ≥10 points.
 - 3.4. Montreal Cognitive Assessment (MoCA): Screening for dementia. Result: 0-30. Exclusion if <26.
4. Complementary questionnaires to complete patient profile:
 - 4.1 Handedness Questionnaire (22)
 - 4.2 Behavioral Inhibition and Behavioral Activation Self Report Scales (BIS/BAS) (23): These scales are used to monitor the perceived sensitivity to reward and punishment. BIS/BAS is broken into four sub-scores: BIS (7 to 28), BAS drive (4-16), BAS fun-seeking (4-16), and BAS reward (7-20).
 - 4.3 Basic sleep habits (bedtime, sleep latency, wakefulness during the night, waking time, total amount of sleep on average, optimal total amount of sleep)
5. The following instructions will be given for the night and following day:
 - 851 How to use the EEG-headband the night before visit 2 (oral and written instructions, including sleep diary); how to use the actigraphy watch.
 - 5.2 To not consume more caffeine than usually. To please not drink alcohol.
6. The participant will be randomized to the respective intervention for visit 2 (either gamma-tACS or first control stimulation).

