Visit 5 (6-9 days after Visit 2; afternoon/early evening, i.e. start between 12pm and 6pm)

The day before: reminder (e-mail/SMS/phone call, depending on the participant's preference) of appointment on the following day - including request to abstain from alcohol and drugs as well as from excessive caffeine consumption.

1. Questioning whether there has been any use of alcohol, psychotropic substances or illicit drugs during the past 24 hours. If yes, the participant is excluded.
2. Questioning if there is a new diagnosis. If yes, the participant will be excluded if the diagnosis meets exclusion criteria.
3. Questions to assess current sleepiness and mood, as this may affect the results of further testing:
 - 3.1 Questions for sleep quality the night before
 - 3.2 Karolinska Sleepiness Scale
 - 3.3 Positive And Negative Affect Schedule (PANAS)
4. Gamma-tACS or controlstimulation (according to randomization) during the following cognitive tests, presented on a computer screen (2 minutes of resting EEG without stimulation after each test):
 - 4.1 Rey Auditory Verbal Learning Test (RAVLT, version 2)
 - 4.2 Letter Fluency; letters F, A, S

- 4.3 Stroop Color and Word Test
- 4.4 Trail Making Test A and B
- 4.5. Word association test; version 2
- 4.6 Four subtests of the Test of Attentional Performance (TAP): Alertness, Go/NoGo, Divided Attention, Visual Scanning
- 4.7 RAVLT delayed recall; version 2
5. Evaluation of side effects with open question (“Did you feel anything particular or note anything special during this session?”)
6. The participant will be given the sleep diary for the third night with the EEG headband.

Visit 6 (day after Visit 5; morning, i.e. start between 8am and 12pm)

1. The participant brings back the EEG-headband (used the night before). Data quality check, review of sleep diary.
2. Questioning whether there has been any use of alcohol, psychotropic substances or illicit drugs during the past 24 hours. If yes, the participant is excluded.
3. Questions to assess current sleepiness and mood, as this may affect the results of further testing:
 - 3.1 Questions for sleep quality the night before
 - 3.2 Karolinska Sleepiness Scale
 - 3.3 Positive And Negative Affect Schedule (PANAS)
4. Cognitive follow-up testing
 - 4.1 RAVLT “ultra-delayed” recall; version 2
 - 4.2 Letter fluency; letters B, H, R
 - 4.3 Stroop Color and Word Test (SCWT)
 - 4.4 Trail Making Test Part A and B
 - 4.5 Word association recall; version 2

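### Visit numbers in section 8.3 do not match the current schedule, so the Aim 1 and Aim 2b rules as numbered point to the wrong sessions

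*Combined protocol and SAP*

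**What the plan says.** Section 8.3, Aim 1: the proportion of participants completing stimulation and cognitive testing "will be calculated after both stimulation sessions, i.e. visit 2 and visit 4".

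Section 8.3, Aim 2b: the secondary outcomes are verbal and associative learning (immediate, delayed and 5-day recall), Letter Fluency, Stroop, Trail Making and the TAP. They are to be compared through the difference "between visit 1-visit 2 and visit 3-visit 4; comparison of absolute results of visit 1 versus visit 3 and visit 2 versus visit 4".

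The schedule says otherwise. The Table of Events (7.1) heads the fourth visit "Visit 4 (telephone; 5 days after Visit 2" and limits its cognitive content: "x (only verbal memory and associative verbal memory recall". Section 7.4 places the second stimulation at Visit 5: "Gamma-tACS or controlstimulation (according to randomization) during the following cognitive tests, presented on a computer screen". At Visit 1 the cognitive-testing cell of 7.1 is empty, and the only cognitive measure in 7.3 is a screening instrument: "Montreal Cognitive Assessment (MoCA): Screening for dementia. Result: 0-30. Exclusion if <26".

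The Synopsis ties Aim 1 to the stimulation sessions without numbering them. The outcome is "Cognitive testing during tACS completed in >80% of participants", and the analysis is the proportion of "participants with completed cognitive testing during stimulation study session".

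**The concern.** These sentences are operative analysis rules. Table 1 marks completion of cognitive testing as a primary outcome for Aim 1, and Aim 2b covers the secondary outcomes. An analyst who follows the numbers would look for a stimulation session in a telephone call. The same analyst would build the Aim 2b contrasts from visits at which each participant has received only one of the two conditions.

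The analyst must therefore decide which visits were meant, and 8.3 gives no consistent key. In the Aim 1 sentence, labels 2 and 4 are stimulation sessions. In Aim 2b, the contrasts make sense only if 1 and 3 are the stimulation sessions and 2 and 4 the next-day sessions. Someone who carries the Aim 1 key into Aim 2b would read the last contrast as performance during stimulation rather than the day after. A choice that the plan should settle could then be made after the data are seen.

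**Working it through.** No sample-size, power or error-rate figure is involved, so the check sets the schedule against the rules.

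**Step 1. What each visit contains (7.1, 7.3, 7.4).**

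| Visit | Type | Period | Study cognitive content |
|---|---|---|---|
| 1 | Baseline | none | None (MoCA screen only) |
| 2 | Stimulation | 1 | Full battery |
| 3 | Next day | 1 | Full battery, memory as recall |
| 4 | Telephone, day 5 | 1 | RAVLT and word-association recall |
| 5 | Stimulation | 2 | Full battery |
| 6 | Next day | 2 | Full battery, memory as recall |
| 7 | Telephone, day 5 | 2 | RAVLT and word-association recall |

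**Step 2. Aim 1.** Stimulation is given at Visits 2 and 5. Section 7.5 lists the on-site visits as 1, 2, 3, 5 and 6, so Visit 4 cannot be a stimulation session. One of the two visits named is wrong.

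**Step 3. Aim 2b, taken as numbered.** The result is the same for either randomised sequence.

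- Visit 1 minus 2 against Visit 3 minus 4: needs Visit 1 scores that are not scheduled, and includes only the first condition.
- Visit 1 against Visit 3: the same two problems.
- Visit 2 against Visit 4: both visits belong to the first condition, and Visit 4 has recall only. This contrast can be formed for RAVLT recall. For word pairs it can be formed only if same-day delayed recall is collected at Visit 2. It cannot be formed for Letter Fluency, Stroop, Trail Making or the TAP.

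So 0 of the 3 contrasts compare gamma with control within a person. None uses Visits 5, 6 or 7. Five-day recall is named as a secondary outcome but has no cross-condition contrast in this list.

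**Step 4. Can one recount of the visits rescue both rules?** Keep the visits in their scheduled order.

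- If labels 2 and 4 are Visits 2 and 5, as Aim 1 needs, label 1 must be Visit 0 or Visit 1. Neither has a study battery or a condition, so label 1 against label 3 cannot compare conditions.
- If label 1 is a visit with study tests, as Aim 2b needs, it is Visit 2 at the earliest. Label 2 is then Visit 3 or later, and labels 2 and 4 cannot be the two stimulation sessions.

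Aim 1 fits a count of on-site visits with baseline as 1. Aim 2b fits a count of on-site visits starting at the first stimulation. No single key satisfies both, and neither of these counts includes the telephone visits.

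**Step 5. Renumbered to the current schedule.** For both sequences, four comparisons contain both conditions within a person: (Visit 3 minus 2) against (Visit 6 minus 5), Visit 2 against 5, Visit 3 against 6, and Visit 4 against 7. The first three cover the full battery, subject to the word-association condition below. The fourth covers RAVLT and word-association recall.

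**Step 6. Word association.** Section 7.4 lists the word association test at Visits 2 and 5 but no separate same-day delayed recall. One Table 1 row scores that test by learning trials 1 to 4 on stimulation days; another lists delayed recall from it on those days. If only learning trials are collected, a change score from Visit 2 to Visit 3 would subtract two different measures.

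**The case against.** The strongest reply is that the comparison is specified, and only its labels are stale. Aim 2b refers back to the tests in Aim 2a, where the ANCOVA has treatment as a within-subject factor and stimulation order as a covariate. The aims table in section 3 names recall after 5 days for gamma against control. Table 1 indexes the tests by condition, with stimulation day, next day and, for memory recall, phone call under A and again under B. All of this stands, and it rules out several stronger readings that a reader might infer:

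- *That no within-person analysis, or no cross-condition analysis of 5-day recall, is planned.* The places just cited show that both are intended. What fails is the list of visit contrasts.
- *That Aim 1 would count someone who left before Visit 5 as complete.* The sentence requires both stimulation sessions, so such a count would contradict its own words. The numbered rule cannot be met; it does not define a different endpoint.
- *That Visits 1 to 4 can yield nothing on the executive and attention tests.* Visits 2 and 3 both carry the full battery, so a between-sequence comparison within period 1 is possible. It is not among the numbered contrasts, however, and does not use the crossover.

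The version table mentions a verbal learning test at Visit 1. That is change-log text; the current 7.1 and 7.3 schedule no such test, so it does not supply the missing Visit 1 scores.

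The reply does not remove the point. The visit references are the part of the rule that an analyst would program, and step 4 shows that 8.3 cannot be repaired by guessing one hidden numbering.

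**Conclusion.** The point holds as a limited but real error in operative rules, and it should be corrected before analysis. One of the two sessions named for Aim 1 is wrong. None of the three Aim 2b contrasts, as numbered, compares gamma with control within a person. Five-day recall is missing from the contrast list, and the two numberings in 8.3 are incompatible.

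The consequences are bounded. The intended comparison can be recovered from the documents. Aim 2a is defined by the day after encoding rather than by visit number, so it is unaffected, and so is the sample size of 28. Section 8.3 also calls the Aim 6 comparison of the same executive and attention tests exploratory.

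The conclusion assumes that 7.1 and 7.4 are the current schedule, which 7.5 supports by listing the same on-site visits. Two nearby matters are separate: which occasions the Table 1 completion row should cover, and whether the telephone visits are required (5.1.2 and 7.5 differ).

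**What to change.** In section 8.3:

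- **Aim 1:** name Visits 2 and 5 as the two stimulation sessions.
- **Aim 2b:** replace the three contrasts with (Visit 3 minus Visit 2) against (Visit 6 minus Visit 5), Visit 2 against Visit 5, and Visit 3 against Visit 6. Add Visit 4 against Visit 7 for 5-day RAVLT and word-association recall.
- **Condition:** state that gamma or control is assigned to each visit from the randomised sequence, so that the contrasts correspond to the A and B occasions in Table 1.
- **Word association:** apply the change-score contrast only if the same measure, same-day delayed recall rather than learning trials, is collected at Visits 2 and 5.

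The cost is an edit to the analysis wording. It needs no new data, visits or participants.

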| Montreal Cognitive Assessment (20) | Ordinal 0-30 | 0 | All | Screening |
| Epilepsy Screening (21) | Binary | 0 | All | Screening |
| Handedness Questionnaire (22) | Laterality Index | 0 | All | Covariate uses |
| Behavioral Inhibition and Behavioral Activation Self Report Scales (BIS/BAS) (23) | Ordinal, 4 subscales: BIS (7 to 28) BAS drive (4-16) BAS fun-seeking (4-16) BAS reward (7-20) | 0 | All | Covariate uses |
| Basic Sleep Habits | hh:mm; hours/min | 0 | All | Covariate uses |
| Stimulation conditions | | | | |
| Epileptiform activity in EEG | Binary | 0 | All | Early termination of study participation |
| Karolinska Sleepiness Scale (24) | Ordinal 1-10 | D1A, D2A, D1B, D2B | Aim 2 | Covariate use |
| PANAS (Positive and Negative Affect Schedule) (25) | Ordinal 20-100 | D1A, D2A, D1B, D2B | Aim 2 | Covariate use |
| Sleep quality night before | Categorical (nominal) | D1A, D2A, D1B, D2B | Aim 2 | Covariate use |
| Cognitive testing | | | | |
| Completed | Binary | D1A, D2A, D1B, D2B | Aim 1 | Primary outcome |
| Delayed and ultra-delayed recall from Rey Auditory Verbal Learning Test (RAVLT) (26) and from word | Ratio (number of correct words); number of correct words for trials 1-5 (=learning), for trial 6 ("interference") and for trial 7 ("recall"); | D1A, D2A, PA, D1B, D2B, PB | Aim 2, Aim 5 | Primary outcome |

| | | | | |
|---|---|----------------------------|-------|---|
| association test; RAVLT encoding | number of confabulations and perseverations in total) | | | |
| Time from encoding of RAVLT and word association test to delayed and ultra-delayed recall | Interval (hh:mm) | D1A, D2A, PA, D1B, D2B, BP | Aim 2 | Covariate use |
| Time from encoding of word association test to delayed and ultra-delayed recall | Interval (hh:mm) | D1A, D2A, PA, D1B, D2B, BP | Aim 2 | Covariate use |
| RAVLT | Ratio (number of correct words for trials 1-5 (=learning), for trial 6 ("interference") and for trial 7 ("recall"); number of confabulations and perseverations in total) | D1A, D1B | Aim 2 | Covariate use |
| Word association test | Ratio (number of correct words for trials 1-4) | D1A, D1B | Aim 2 | Covariate use |
| Letter Fluency (28) | Ratio (number of correct words, number of perseverations and number of rule breaks) | D1A, D2A, D1B, D2B | Aim 6 | Secondary outcome |
| Stroop Color and Word Test (29) | Interval (sec), ratio (errors) | D1A, D2A, D1B, D2B | Aim 6 | Secondary outcome |

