| Trail Making Test A and B (30) | Interval (sec), ratio (errors) | D1A, D2A, D1B, D2B | Aim 6 | Secondary outcome |
| Test of Attentional Performance (TAP) (31) | Interval, ratio (Alertness: Percentile rank of median reaction time for correct responses, percentile rank of standard deviation; Go/NoGo: Percentile rank of median reaction time for correct responses, percentile rank of standard deviation, percentile rank of errors; Divided Attention: Percentile rank of median reaction time for correct responses, percentile rank of standard deviation, percentile rank of errors, percentile rank of omissions; Visual Scanning: Percentile rank of median of critical and non-critical, respective standard deviation, omissions) | D1A, D2A, D1B, D2B | Aim 6 | Secondary outcome |
| Sleep EEG | | | | |
| First night with ≥4 hours of recording | Binary (hh:mm) | N1 | Aim 3 | Primary outcome; early termination of study participation if <4 hours |
| EEG worn for ≥4h hours in 3/3 nights | Binary (nights) | N1, N2A, N2B | Aim 3 | Primary outcome |

| | | | | |
|---|-------------------------------------|--------------------|--------------|---------------------|
| Sleep latency | Minutes | N1, N2A, N2B | Aim 4, Aim 5 | Covariate use |
| Sleep efficiency | % | N1, N2A, N2B | Aim 4, Aim 5 | Covariate use |
| Sleep spindles, slow wave sleep | Amount/hour | N1, N2A, N2B | Aim 4, Aim 5 | Primary outcome |
| Subjective tolerability of headband | Binary, nominal | N1, N2A, N2B | Aim 3 | Exploratory use |
| Actigraphy | | | | |
| Motor activity/24 hours, resting time for sleep | %, hours | N2A, D2A, N2B, D2B | Aim 7 | Exploratory outcome |
| Thresholding | | | | |
| TMS motor threshold | % MSO (maximal stimulator output) | D2A | Aim 8 | Exploratory outcome |
| tACS thresholding | mA (lower value of 21 Hz and 40 Hz) | D2A | Aim 8 | Exploratory outcome |
| Safety Monitoring | | | | |
| AEs and SAEs documentation | Events | All | All | Safety monitoring |

¹ Units of measurement or the scale.

² Occasions of evaluation or retrieval:

S = Screening

0 = Enrollment and Baseline

N1 = Night 1

D1A = Day 1 in Intervention A

N2A = Night 2 in Intervention A

D2A = Day 2 in Intervention A

PA = Phonecall in Intervention A

D1B = Day 1 in Intervention B

N2B = Night 2 in Intervention B

D2B = Day 2 in Intervention B

PB = Phonecall in Intervention B

³ The specific aims in which the variable will play a role in data analyses.

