8.4 Planned Interim Analyses

No interim analyses will be performed.

9. Sample Size Rationale

We plan to recruit 28 healthy adults in this feasibility study (primary outcome). The sample size was computed such that the study has 95% power (alpha = 0.05) to reject the null hypothesis that 50% of the population of interest can complete the study procedures for an effect size of $g = 0.3$, meaning that if at least 80% of the study sample complete the procedures, feasibility in the population of at least 50% is established.

10. Data Capture and Database Management

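### Table 1 and Section 8.3 disagree on which recall outcomes are primary, and 8.3 tests two day-after scores under one null hypothesis at 0.05 with no decision rule

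*Combined protocol and SAP*

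**What the plan says.** Section 8.3, Plans for Aim 2, item a: "Primary outcome: Ultra-delayed verbal memory recall (i.e. amount of words and word associations remembered the day after encoding the RAVLT". One null hypothesis follows, of no difference in day-after recall, with a directional alternative favouring gamma-tACS. Item b of the same plan lists "Secondary outcomes: Verbal and associative learning (immediate and delayed recall, recall after 5 days" and the executive tests.

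Table 1 (Section 4.3) has a row for "Delayed and ultra-delayed recall from Rey Auditory Verbal Learning Test (RAVLT) (26) and from word" association, with occasions, aims and role given as "D1A, D2A, PA, D1B, D2B, PB | Aim 2, Aim 5 | Primary outcome". The occasions are the stimulation day, the day after and the telephone call, in both conditions. Table 1 gives the same role to "Sleep spindles, slow wave sleep | Amount/hour", to completion of cognitive testing, to the first EEG night, and to "EEG worn for ≥4h hours in 3/3 nights".

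Section 8.1: "All testing described below assumes a significance threshold of" 0.05. The only multiplicity adjustment in the plan is the Bonferroni correction in 8.3, and it covers post-hoc tests.

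Section 9: "We plan to recruit 28 healthy adults in this feasibility study (primary outcome"). It justifies 28 on feasibility (50% against 80% completion, 95% power). Section 5.1.2 justifies 28 on dz = 0.5, 80% power and alpha 0.05. It also counts Visits 4 and 7, the five-day telephone recalls, among the visits for the primary outcomes. Section 7.5 says those two visits are not mandatory.

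**The concern.** Two things are unsettled in the current text.

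First, same-day and five-day recall are primary in Table 1 and secondary in 8.3. A reader cannot tell from the plan which label binds.

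Second, 8.3 itself puts two scores under one hypothesis. The synopsis, the aims and the outcome table list verbal memory and associative memory separately, as (a) and (b), and no scoring rule adds up to 15 words and up to 8 word pairs. The false-positive rate of the primary memory claim depends on a rule that the plan does not give.

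The labelling also affects who counts as a completer. Section 5.1.2 defines the final 28 by the visits needed for the primary outcomes, and whether the telephone visits belong there depends on whether five-day recall is primary.

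**Working it through.** **1. The plan's own sample sizes.**

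- Feasibility, exact one-sided binomial, n = 28, rejecting at 19 or more completers: P(X ≥ 19 | 0.5) = 0.0436 and P(X ≥ 19 | 0.8) = 0.961. Power is 0.941 at n = 26 and 0.926 at n = 27. Section 9 reproduces.
- Efficacy, paired t-test, dz = 0.5, noncentrality 0.5 × √28 = 2.65 on 27 df. One-sided at 0.05, power at 28 is 82% and 27 participants suffice for 80%. Two-sided at 0.05, power at 28 is 72% and 34 are needed. The 80% in 5.1.2 therefore reproduces only as a one-sided test. The plan states no sidedness, though its alternative is directional.

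Both calculations support 28. The efficacy one describes a single paired comparison.

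**2. The two day-after scores in 8.3, each at 0.05.**

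- Both required: the error is at most 0.05.
- One composite score: the error is 0.05.
- Either suffices, independent: 1 − 0.95² = 0.0975.
- Either suffices, correlation ρ, two-sided: 1 − P(|Z1| < 1.96, |Z2| < 1.96). The documents give no ρ, so a range is assumed.

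| ρ | 0.3 | 0.5 | 0.7 | 0.9 |
|---|---|---|---|---|
| two-sided | 9.5% | 9.1% | 8.4% | 7.0% |
| one-sided | 9.3% | 8.8% | 8.0% | 6.8% |

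**3. If Table 1 governed.** Count one recall score per test and occasion. Table 1 then gives 2 tests × 3 occasions + spindles + slow wave sleep = 8. The visit lists in 7.4 schedule delayed RAVLT recall at Visits 2 and 5 but no same-day delayed word-pair recall, so seven are actually scheduled. The error is the chance that at least one is significant at 0.05, two-sided, with a common assumed correlation.

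| Tests | independent | 0.3 | 0.5 | 0.7 |
|---|---|---|---|---|
| 7 | 1 − 0.95⁷ = 30% | 27% | 23% | 18% |
| 8 | 1 − 0.95⁸ = 34% | 30% | 25% | 19% |

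**4. Cost in power of each repair** (n = 28, dz = 0.5 for each score).

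| Rule | one-sided | two-sided |
|---|---|---|
| One score at 0.05 | 82% | 72% |
| Alpha split, 0.025 each, power per test | 72% | 61% |
| Both required at 0.05 each | 65% to 82% | 45% to 72% |

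The last row uses only the bounds: power to win on both lies between 2 × (power per test) − 1 and the power per test, so 2 × 0.825 − 1 = 0.65 and 2 × 0.723 − 1 = 0.45.

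**The case against.** The strongest reply is that 8.3 is the operative analysis text. It fixes the day-after time point in both the outcome and the null, and expressly makes same-day and five-day recall secondary. On that reading only the combination of words and word pairs is open, and one outcome name with one null could mean one combined result, with error at most 5%. This is fair as far as it goes. It removes the inflation only if that rule is written down, and no rule is. Nor does it remove the contrary labels in Table 1, and 5.1.2 follows the broader version.

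Three stronger readings are tempting, and the documents do not support them.

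- A reader might infer that Section 9 contradicts 8.3 by calling feasibility primary. It need not. Table 1 assigns primary status aim by aim, 5.1.2 speaks of primary outcomes in the plural, and a feasibility primary beside an efficacy primary is normal in a pilot. What is missing is a statement of how they relate.
- A reader might quote 34% as the trial's error rate. It assumes independence, Table 1 overriding 8.3, and a same-day word-pair recall that the visit lists do not contain. Recall scores from the same people will probably be correlated, so it is an upper figure.
- A reader might conclude that splitting alpha takes power from 72% to 61%. That is the two-sided case only. The plan's own 80% fits a one-sided test, where the fall is from 82% to 72%.

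The stakes are also limited. Section 2.2 says an effect on memory or sleep EEG is not needed for the later trial, and 8.1 cautions against over-reading p-values. Section 8.1 nevertheless declares significance at 0.05, so the primary claim still needs a defined error rate.

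**Conclusion.** The point holds in this form: Table 1 and 8.3 conflict on same-day and five-day recall, and 8.3 leaves open how its two day-after scores decide one hypothesis. Depending on the unstated rule, the false-positive rate of the primary memory claim runs from at most 5% to 9.8%. The inflated end applies only if either score can carry the claim, and the intermediate values rest on assumed correlations. The 30% to 34% range is conditional on Table 1 governing and on independence.

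The sample size of 28 is not shown to be wrong. It reproduces on feasibility and on one-sided efficacy. This should be corrected before analysis, but the go/no-go for the later trial does not depend on it.

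**What to change.** - In 8.3 and Table 1, name one primary efficacy outcome at the day-after time point. RAVLT words alone would do, and costs no power. The documents treat words and word pairs as parallel, so choosing between them is the sponsor's decision.
- Alternatively, keep both scores and state the rule: either with alpha control, both required, or a defined composite. The power cost is in the last table of the working.
- State whether the test is one- or two-sided.
- Relabel same-day recall, five-day recall, spindles and slow wave sleep as secondary in Table 1.
- State in Section 9 that feasibility is a separate primary objective, judged on its own proportions.
- Reconcile 5.1.2, which counts Visits 4 and 7 among the visits for the primary outcomes, with 7.5, which makes them non-mandatory.

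The cost is editing. No participants, visits or data are added. The downside is that the relabelled outcomes lose primary status.
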